**Specific Aim 4b. Haptoglobin phenotype**

We will test the hypothesis that haptoglobin 1-1 predicts better outcome. For our analysis of haptoglobin, patients will be categorized as Hp1-1, 1-2, or 2-2 phenotype. Our primary analysis will examine whether Hp1-1 predicts a higher likelihood of good neurologic outcome (defined as above) using a chi-square test. Our preliminary data suggests that that 13% of patients will have the Hp1-1 phenotype, 48% will have Hp 1-2, and 38% will have 2-2. We do not anticipate interaction between haptoglobin genotype and treatment effect; therefore, the analysis will be conducted combining the two treatment arms. Assuming a sample size of 65 and 435 for Hp1-1 and Hp (1-2 + 2-2), respectively, the study will have 82% power to detect a difference of 19% (46% for the Hp 1-1 group and 27% for the other 2 genotypes) with a 0.05 two-sided significance level.

**Specific Aim 5. Leukocyte infiltration and outcomes.** Our preliminary data from both mice and human patients demonstrates a robust recruitment of peripheral leukocytes into the hematoma and perihematoma region over the first seven days after ICH. During this time, blood derived macrophages transition from a pro-inflammatory phenotype to a reparative phenotype that aids in phagocytosis of the hemorrhage and wound healing. Cell surface markers on macrophages involved in phagocytosis, including CD36, and inhibition of T cell response, including PDL2, increase over this time. Our primary hypothesis is that this transition to repair is critical to good outcome after ICH, and that patients who transition to reparative macrophage profiles and shifts from effector to regulatory T cell responses earlier after ICH onset will have improved outcomes.

Hematoma aspirate and blood samples will be shipped ambient priority overnight to Yale University and immediately analyzed to prevent degradation of samples. Mononuclear cells will be isolated by Ficoll gradient, stained with fluorophore-conjugated antibodies to CD45, CD11b, CD16, CD3, CD4, CD8, CD25, and CD127. Leukocytes will be quantified by flow cytometry and cell sorting (FACS) to isolate populations of interest (see Table below for the gating of the populations to be sorted). In a single batch, RNA from each population of interest will be converted to cDNA and analyzed by RNAseq to fully characterize the transcriptional profile of

## 8. Risks

**Blood draws:** There are no known medical risks to the patient except those associated with a blood draw from an indwelling line or a peripheral blood draw (both medical and surgical arms). We have minimized the number of blood draws so that they are timed with routine blood draws or with hematoma fluid aspiration and this will occur through an existing in-dwelling line or peripheral blood draw.

**Drainage collection:** In the surgical arm, the hematoma drainage in patients with a brain catheter will initially be obtained as part of its placement in the operating room during which the blood clot is aspirated as part of the MISTIE III parent protocol. This poses no additional risk or exposure of the volunteer to additional procedures. The subsequent samples will be collected daily from the spontaneous hematoma drainage into the collection bag/chamber using sterile technique. The only risk is infection, which is minimal for both hematoma fluid and peripheral blood collection.

No additional CT scans are required.

There are no legal ramifications to the participant.

There are no financial risks to the participant.

All unanticipated problems or study deviations will be reported to the PI who will be responsible for reporting them to the IRB.

### **9. Benefits**

This may result in improved treatment of ICH for society in general. The participant will have the satisfaction of helping others through their participation.

### **10. Payment and Remuneration**

There are no forms of compensation to the participant. The participants' care and ability to participate in the MISTIE III trial will not be impacted if they decide not to participate in this ancillary study.

### **11. Costs**

There are no costs to the patients. Any costs associated with the blood draw will be paid by the investigator. The imaging will be done as part of the MISTIE III protocol.

1.0. Statistical Analysis Plan and Statistical Reports

This chapter provides the details of statistical considerations, analyses, and reports planned for the MISTIE III Trial, including proposed regression models, sample size estimates, power considerations, interim analyses, and analysis of adverse events. The proposed analyses will be conducted on the whole patient sample and on subsets of patients defined by gender, race, and ethnicity as well as patient-specific clinical factors/categories and treatment categories. In addition, this chapter discusses statistical issues relevant to these analyses (e.g., sample data to be used, missing data, adjustments for multiplicity, etc.).

Initially, the Data Coordinating Center (DCC) will examine data quality, create secondary variables, and perform exploratory data analyses (EDA). All variables will be evaluated to detect gaps, patterns, and inconsistencies in the data. These analyses will emphasize examination of the nature and extent of variability for all variables. Visual techniques to explore continuous variables will include stem-and-leaf plots, box plots, and quantile-quantile plots. Outliers will additionally be examined for data entry errors. Summary statistics for continuous variables will include the number of patients, median, mean, standard deviation, and range, while statistics for categorical variables will include the frequency and percentage of patients in each category.

Statistical analyses will be performed on data that have been quality-assured through DCC protocols and monitoring reviews, and that have been exported by the DCC directly from the MISTIE III database. The following analysis procedures may be applied to blinded (no treatment arm designation, for study investigators and staff), partially unblinded (treatment designation only as "A" and "B," for DSMB and at interim analyses), and unblinded (full treatment designation, for final analyses) data, by DCC staff having the appropriate role permissions.

The MISTIE III Executive Committee receives the open DSMB reports.

2.0. Objectives of the Study

2.1. Efficacy

The primary aim of this multicenter, international, randomized, open-label, phase 3 trial is to determine the efficacy of intra-clot catheter placement and aspiration of hematoma contents, followed by gentle clot irrigation with low dose recombinant tissue plasminogen activator (rt-PA), referred to as Minimally Invasive Surgery plus rt-PA (MIS+rt-PA). The primary hypothesis of this trial is that the MIS+rt-PA approach to intracerebral hemorrhage (ICH) management will result in more patients having overall better functional outcome at 365 days, as defined by the proportion of subjects with dichotomized, adjudicated modified Rankin Scale (mRS) score 0-3 vs. 4-6, when compared to the mRS scores for patients managed with standard aggressive medical treatment. Although the mRS includes a category for death, and hence the primary analysis incorporates mortality outcomes, in-hospital and 30-day mortality will also be examined as safety outcomes for the trial. Furthermore, 365-day mortality will be evaluated separately as a secondary efficacy outcome. An intent-to-treat (ITT) paradigm for the analyses will be incorporated. The MISTIE III trial will enroll a total of 500 eligible patients, 250 randomized each treatment arm (MIS+rt-PA or medical management). The power to detect (88%) is for an estimated effect size of 13% across all clot locations with this sample size (500).

Additional analyses of efficacy outcomes will evaluate the therapeutic benefit of MIS+rt-PA relevant to medical management in improving subjects' function and quality of life at 365 days post symptom onset as measured by extended Glasgow Outcome Scale (eGOS), days in various locations such as home

Minimally Invasive Surgery Plus rt-PA for ICH Evacuation Phase 3

during the 365-day period, patient disposition at 180 and 365 days including proportion of days in longterm care facilities, National Institutes of Health Stroke Scale (NIHSS), Barthel score, days in hospital, days in intensive care unit (ICU), Stroke Impact Scale (SIS), Preference-Based Stroke Index (PBSI), EuroQol-5 Dimension (EQ-5D), Mini-Mental State Examination (MMSE), Personal Health Utility Interview, and Center for Epidemiological Studies – Depression (CES-D).

2.2. Efficacy Measures Summary: All Analyses Adjusted Similarly to the Primary Analysis

- **Primary Efficacy Analysis:** Dichotomized, adjudicated, cross-sectional mRS 0-3 vs. 4-6 at 365 days post-ictus, adjusting for baseline (pre-randomization) variables used in covariate adaptive randomization as well as the clinically established severity variables IVH size and ICH location (lobar or deep).
- Additional, Exploratory Analyses of mRS at 365 days:
 - a. Dichotomized, adjudicated, cross-sectional mRS 0-3 vs. 4-6 at 365 days post ictus, adjusting for baseline (pre-randomization) variables used in covariate adaptive randomization as well as additional baseline variables determined to be associated with the outcome.
 - b. Ordinal, adjudicated mRS (0-6) at 365 days.
 - c. mRS 0-3 vs. 4-6 at 365 days based on a full longitudinal analysis of the mRS data at 90, 180, and 270 days.
 - d. Severity subgroup analyses (including, but not limited to, IVH size, location of ICH, presentation co-morbidities such as diabetes, CVD, and white matter disease, etc.)
 - e. Cross-sectional of mRS 0-3 vs. 4-6 for demographic subgroups of patients, including for race and gender. (For d and e, see section 5.5.)
 - f. Analysis of cross-sectional mRS 0-3 vs. 4-6 at 365 days that models random effects for hospital sites.

• Secondary Analyses of other outcomes

- 1. Dichotomized eGOS UGR-US vs. LS-Death at 365 days.
 - Subordinate: Ordinal eGOS UGR, LGR, MD, LM, US vs. LS, VS, Death at 365 days.
- 2. All-cause mortality longitudinally from ictus to 365 days.
 - Subordinate: Predictors of mortality.
- 3. Relationship between clot removal as an AUC clot-assessment that estimates the timeweighted clot volume from ictus to end of treatment (EOT; i.e., 24 hours after last dose) as AUC clot exposure and functional outcome (proportion 0-3 mRS).
- 4. Patient disposition:
 - a. Home days over 365 days' time from ictus.
 - b. Patient location at 365 days post ictus (i.e., good vs. bad location. See Tertiary 2g for definition.)
- 5. 180-day efficacy:
 - a. Dichotomized, adjudicated, cross-sectional mRS 0-3 vs. 4-6.
 - Subordinate (1): Ordinal, adjudicated mRS (0-6).
 - b. Dichotomized, adjudicated eGOS UGR, LGR, MD, LM, US vs. LS, VS, Death.
 - Subordinate (2): Ordinal, eGOS UGR, LGR, MD, LM, US vs. LS, VS, Death.
 - Subordinate analyses 2-5 as defined under the Primary but for eGOS.
- 6. Type and intensity of ICU management:
 - a. ICU days

Minimally Invasive Surgery Plus rt-PA for ICH Evacuation Phase 3

- b. ICU management (ICP, Ventilation, BP support, osmotherapies)
- c. Hospital days
- 7. EQ-VAS and EQ-5D

• Tertiary (exploratory/sensitivity):

- 1. Functional status at 180 and 365 days post-stroke:
 - a. GOS
 - b. Barthel Index
 - c. NIHSS
 - d. MMSE
- 2. Quality of life at 180 and 365 days post-stroke:
 - a. SIŚ
 - b. PBSI
 - c. Personal Health Utility Assessment Interview
 - d. CES-D
 - e. EQ dimensions individually assessed
 - f. Home days (180 only)
 - g. Patient location including proportion of days in home, rehabilitation, acute care, longterm care facilities. These will be evaluated by individual location type and dichotomized as good vs bad outcome defined as home and rehabilitation vs acute care, long-term care and death.
 - h. Proportion of subjects in vegetative condition
- 3. Cost-benefit model

In addition to the primary, secondary, and tertiary (exploratory) measures, there are a number of related and intermediate surrogate outcomes of interest, including time to treatment, surgical task descriptors, clot locations, Glasgow Coma Scale (GCS), Graeb Scale, clot lysis rate and final clot size reduction.

2.3. Safety

The safety of MIS+rt-PA relative to medical management is assessed by comparing the proportion of subjects between the two groups with treatment-related SAEs within the 30-day time frame: mortality, rebleeding, infection, and first-week (designated as operative mortality for the surgical group) mortality. Additionally, the number and proportion of all SAEs across the entire time frame in the respective randomized groups will be evaluated starting with the follow-up time frames of 180 and 365.

Interim safety analyses will be prepared for the external Data Safety and Monitoring Board (DSMB) on a pre-arranged schedule (such as semi-annual or after enrollment of a fixed number of subjects) to evaluate efficacy and safety. Safety measures include: monitoring the incidence of symptomatic and asymptomatic intracranial bleeding events (i.e., hemorrhage extension, new hemorrhage, catheter-tract hemorrhage) through daily computed tomography (CT) scans for the first four days after randomization and then repeated one day (approximately 24 hours) after ICH catheter removal, and monitoring the incidence of confirmed and suspected infection and in-hospital mortality.

2.3.1. Safety Measures Summary

- Mortality and safety events at 30 days post-randomization:
 - a. First-week (operative) mortality
 - b. All-cause mortality

- c. Symptomatic bleeding rate
- d. Infection rate
- e. Total SAEs at 30 days
- f. Summary of AEs and SAEs by MedDRA code and grouped by organ system

2.3.2. Safety Monitoring and Recruitment Suspension Rules

Safety events above pre-specified thresholds will trigger a "suspend recruitment and review" by the DSMB to investigate the presumed cause and impact of these events. Such events are initially reviewed by DCC staff to determine if an event threshold has been reached at which time the study investigators and the DSMB will be notified. The thresholds triggering such a review are: 30-day mortality >60%, a MIS+rt-PA–related symptomatic bleeding rate >25% (during active treatment or during the 72 hours after treatment will be monitored), first-week operative death rate >10%, and a procedure-related infection rate >15% (over the initial 30 days). If any of these SAEs are attributable to the intervention (catheter insertion or manipulation, or rt-PA injection), the study will be suspended for a complete safety review.

Interim analyses for efficacy will occur after 375 subjects are enrolled and 180 days outcomes are available. These analyses will be based on O'Brien-Fleming stopping boundaries for efficacy and more aggressive (i.e., more likely to stop if there is no early signal of benefit) stopping boundaries for efficacy and safety analyses will be every six months or at other intervals as determined by the external DSMB.

3.0. Study Design

This study is a phase 3, 1:1 randomized, open-label, multicenter evaluation of MIS and ICH lysis with rt-PA versus medical care. The study (n=500) will evaluate the efficacy and safety of MIS plus 1 mg of rt-PA administered every eight hours for up to nine doses as compared to subjects treated with conventional medical management.

4.0. Sample Size Determination for the Primary Efficacy Analysis

The MISTIE phase 2 results, for all available data (non-randomized trial-standardized "pilot" and randomized participants), demonstrated an estimated absolute increase in the probability of achieving an mRS 0-3 of 13.0% [95% CI: (0.4% to 26.4%)] comparing MIS+rt-PA treatment versus medical management 180 days post-stroke.¹ For the intention-to-treat (ITT) analysis, when only randomized patients are considered (n=96), the estimate for the unadjusted treatment effect is 10.9% [95% CI: (-8.8% to 29.4%)], and 16.2% [95% CI: (0.3% to 32.3%)] after adjusting for baseline clinical characteristics. This range of estimates provides a strong motivation for conducting MISTIE III to confirm these clinically beneficial findings. The analogous unadjusted and adjusted effect sizes based on non-lobar ICH patients are very similar to these effect sizes. The second stage of MISTIE II provided evidence of increasing frequency of mRS scores in the 0-2 categories between 180 and 365 days with an unadjusted proportion of mRS 0-3 increasing to 14%. The sample size was selected based on 180-day outcomes in MISTIE II.

It was decided to change the primary outcome to be based on 365-day outcomes because of the lack of a plateau in good functional outcome at 180 days.

5.0. Definition of Study Samples

5.1. Target Population

The target population to which the MISTIE intervention or conventional medical management may be applied are patients with site-determined ICH \geq 30 mL and not requiring extraventricular drainage (EVD) for the management of acute obstructive hydrocephalus.

5.2. Intent-to-Treat (ITT) Sample

As the primary analysis, all efficacy and safety outcome measures are analyzed under the ITT. Under this principle, each eligible subject is analyzed according to the treatment group to which they were assigned at the time of randomization. A total of 500 eligible subjects will be randomized. *Exposure to the MISTIE procedure will be considered evidence of intention to treat.*

5.3. Safety Analysis Sample

All randomized subjects are included in the safety analysis sample. Further safety analyses may be determined by clinical events and subgroups of the surgical task.

5.4. As-Treated Sample for MIS+rt-PA

The potential for cross-overs to the MIS+rt-PA treatment in this study is minimal; none occurred in our prior experience. However, in the case of cross-overs, a per-protocol sample will be constructed and examined in which treatment-as-received is analyzed.

Given that amount of clot resolution is a potentially treatment-related post-randomization variable, this covariate will be examined as an important potential mediator of final outcomes as part of a per-protocol analysis. This treatment performance variable will be explored at the protocol thresholds of 15 mL, and 10 mL and the observed level of 5 mL. Other thresholds may be explored as determined by inspection of the data and clinical findings. Surgical performance will be evaluated by chosen trajectory, surgical experience level and compliance with Surgical Center recommendations, and by actual task performance versus planned performance.

5.4.1. As-Treated Sample for Any Form of Surgery

Given the lack of guidelines to indicate whether any form of surgery is beneficial, different combinations of surgical versus medical therapy will be explored, starting with all subjects receiving any surgical procedure versus all subjects receiving only medical therapy. Important groups that represent actual practices and the timing of such practices occurring will be explored. Given that clot resolution is a potentially treatment-related post-randomization variable, this covariate will be examined as an important potential mediator of final outcomes as part of the as-treated analysis.

Given the absence of clinical trial demonstration of benefit of craniotomy, we will assess the benefit of craniotomy or not by comparing all subjects receiving craniotomy versus those receiving only MIS+rt-PA and those receiving only medical therapy. Craniotomies will be divided into subgroups by time performed (in equal size groups and by day and half day). Finally, we will consider all craniotomies as salvage and assign them to death, then determine the frequency at which they are "life saving."

Minimally Invasive Surgery Plus rt-PA for ICH Evacuation Phase 3

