## 2 BACKGROUND

### 2.1 Rationale

**Scope of Problem:** Brain hemorrhage is a worldwide problem without strategies for treatment or prevention. Its incidence is persistent and its prevalence keeps increasing with an aging population. The high burden of disease is well-established with a 30-day mortality of approximately 40%. Substantial health disparities exist, with an increased incidence for Asians, African-Americans, Hispanics, those without access to blood pressure (BP) management, and the aged.

ICH affects a young and productive population with morbidities that produce disastrous economic and social consequences, and functional impairment produces an intolerable degree of dependency. When hemorrhages of all sizes are considered, only 10%-25% return to functional independence, and functional performance is likely to be much worse ( $\leq 10\%$ ) when initial hematoma volumes are greater than 20-30 mL.

We deliver care in a default position, where we provide complex brain monitoring and ICU support without evidence of benefit or emphasis on mitigation. The state of care for ICH is similar to care for ischemic stroke three decades ago—care is frequently not rendered. When rendered, it is palliative and supportive of cardiorespiratory function rather than reversing the brain injury. The absence of an evidence-validated treatment is associated with high cost, variability in care, uncertainty in decision-making, unacceptable mortality rates, and long-term functional dependency requiring skilled nursing. The ICU stay for a patient with a moderately sized ICH ( $>30$  mL) averages a month, requiring prolonged ventilation, nutrition support, and acute cardiovascular and infection treatments. Health professionals make widely variable treatment, level-of-care, and prognostic decisions without trial evidence or consideration of long-term survivor benefit/burden.

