**MISTIE II Trial Design:** Stage 1 escalated the rt-PA dose (0.3 mg Q8hr, Tier 1 increased to 1.0 mg Q8hr, Tier 2) to test for dose response and safety. When compared to controls, both doses increased clot removal with no difference in bleeding rate (7% vs. 9%), leading to a decision to use the 1.0 mg dose. Tier 3 used the same precise image localization but a wider cannula and higher negative pressures (up to 300 mmHg) and is identified as the “ICES” Tier. We report on 123 subjects (117 MISTIE & medical; 6 ICES, medical only).

**MISTIE II Trial Safety:** The MIS+rt-PA procedure was evaluated for safety by dose, trial stage and comparison to medically treated subjects as defined by the MISTIE protocol utilizing AHA ICH guidelines. All emergent and ICU care was rendered according to guideline for each subject independent of randomization status. Of note, the influence of the withdrawal of care occurred equally among randomized subjects (surgical, 13%; medical, 10%).

**Mortality:** Data on intention-to-treat (54 surgical, 42 medical, n= 96) and all subjects (27 pilot, 96 randomized, n= 123) are provided. Including pilots, 81 subjects underwent MIS+rt-PA. There were no intra-operative deaths. Seven-day mortality was chosen as the immediate post-operative period; mortality was 2% in the MISTIE II cohort, comparing favorably to the 7-day mortality in FAST (12%-14%). The two deaths were related to the severity of the primary bleeding event, with cause of death preoperative respiratory failure (case1) and pre-existing coronary artery disease leading to postoperative myocardial infarction (case2). Thirty-day mortality was 10% and 15% for the medical and surgical groups respectively. No differences were noted for mortality at any time point, for the intention-to-treat, or the total group (Fig. 2). Withdrawal of care was equal in each group (36% vs. 53%) as well as the withdrawal of care temporal profile.

**Figure 2.** Kaplan Meier plot of mortality for randomized MISTIE II subjects. No differences were noted for mortality at any time point. Withdrawal of care was proportionally similar in both groups, and occurred at similar time frames in each group (Fischer's Exact Chi Square; non-significant).

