Interventions include: 1) head positioning (usually 30° elevation HOB), 2) euthermia with core temperature  $\leq 38^\circ$ , 3) normoxia and normocapnia, and 4) sedation and analgesia, to maintain HR  $\leq 120$  with concurrent absence of agitated motor activity. When standard interventions are not effective, mannitol in doses of 1 gm/kg load and 0.25 gm per kg maintenance will be administered. In response to acute sustained ICP elevation ( $\geq 40$  mm Hg or refractory ICP elevation), hyperventilation to a PaCO2  $\leq 25$  mm Hg will be performed. Ventilation parameters, including FiO2 and tidal volume, respiratory rate, and ventilation mode, will be set to produce SaO2 > 90% saturation and mean airway pressures  $\leq 20$  cm H2O. Prolonged sedation with propofol will be used for transient or sustained ICP  $\geq 30$  mm Hg, where agitation is deemed a possible factor. Surgical management of uncontrollable ICP to control ICP is allowed but not encouraged in the absence of full medical therapy. Surgery may be considered if hemorrhage extension or rebleeding occurs, if ICP  $\geq 30$  mmHg, with optimal medical management, for acute compartment syndrome, or other life-saving consideration. When ICP is controlled at  $\leq 20$  mm Hg for one or more days, sequentially withdraw treatment modalities from highest level of intervention to lowest level of intervention. Every effort will be made to avoid long term hyperventilation, in keeping with the AANS head injury guidelines (American Association of NS: Guidelines for the management of severe head injury. Brain Trauma Foundation, American Association of Neurological Surgeons, Joint Section on Neurotrauma and Critical Care. *J Neurotrauma* 13:641-734, 1996) and the ASA ICH treatment guideline statement. (Broderick JP, Connolly S, Feldman E: Guidelines for the management of spontaneous intracerebral hemorrhage: a statement for healthcare professionals from a special writing group of the Stroke Council, American Heart Association. *Stroke* 38:2001-2023, 2007)

ICP monitoring devices will be removed when ICP is maintained < 20 mm Hg without pharmacological therapy.

2. Neurological status: The GCS goal is 15 or 10T sustained for 8 hours of observation. Sedation will be used for agitation. The sedations of choice are Propofol or Lorazepam

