13.2.1. Subordinate, Secondary Efficacy Analysis 2: Predictors of Mortality Analysis

Additionally, survival models will be constructed to examine the mortality, morbidity, and ICU distributions for the MIS+rt-PA and medical management groups. Standard Cox proportional hazard models will initially be examined. These models are commonly written as:

$$h_i(t) = \lambda_0(t) \exp(\gamma X + \phi \cdot TRT)$$

where $\lambda_0(t)$ is a non-parametric baseline hazard function, γ is again a vector of regression coefficients related to the X covariates, and ϕ is the parameter for the treatment effect of EVD plus rt-PA on the hazard of death (mortality). This model may be extended by including time-dependent covariates and non-proportional hazards as deemed necessary through diagnostic checks. Observed mortality will also be compared with predicted mortality based on clinical presentation, overall, and by treatment group. Predicted mortality will be estimated. We will develop a severity model for predicting mortality based on the Tuhrim model.^{2,7,8}

13.3. Secondary Efficacy Analysis 3: Relationship Between Clot Removal as an AUC that Estimates the Time-Weighted Clot Volume from Ictus to EOT as AUC Clot Exposure and Functional Outcome (Proportion 0-3 mRS)

EOT clot volume and/or percent EOT ICH reduction are related to mRS functional outcome regardless of treatment. Based on the experience of the CLEAR III trial, time-weighted average clot volumes will also be considered as a potential predictor of mRS outcome. The null hypothesis is that ICH clot reduction time course (time weighted clot volume, EOT clot volume, and/or percent EOT clot reduction) has no effect on functional outcome regardless of treatment.

In addition, since a "plateau" or "floor" effect of clot resolution over time is likely, subsequent models to statistically test for these fixed effects will consider clot resolution in non-linear terms, such as linear or restricted cubic splines and other non-linear functions. Placement of knots for the splines will be based on the visual inspection of the average ICH trajectory over time. In addition, when using restricted cubic splines, we will consider placing the knots at equally spaced percentiles of the "follow-up time" variable's marginal distribution as recommended by Harrell.⁹ Alternative methods that quantify the time-weighted clot volume will also be considered in this model.⁷

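### The life-saving frequency for craniotomy in SAP 5.4.1 is survival after craniotomy under another name, and cannot tell a useful operation from a useless or harmful one

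*SAP*

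**What the plan says.** SAP 5.4.1 (As-Treated Sample for Any Form of Surgery) sets out two analyses of craniotomy. The first assesses benefit by "comparing all subjects receiving craniotomy versus those receiving only MIS+rt-PA and those receiving only medical therapy", with craniotomies also grouped by when they were done. The second, which closes the section, reads "we will consider all craniotomies as salvage and assign them to death, then determine the frequency at which they are" life-saving. For this second step the SAP defines neither life-saving nor a comparison group, and it gives no death rate without craniotomy other than the assigned 100%.

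Protocol Appendix 3, item 1, describes when surgery may be used in either arm. It says "Surgical management of uncontrollable ICP to control ICP is allowed but not encouraged in the absence of full medical therapy". It then says "Surgery may be considered if hemorrhage extension or rebleeding occurs", and continues with ICP of 30 mmHg or more under optimal medical management, acute compartment syndrome, "or other life-saving consideration".

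Elsewhere the SAP plans to compare observed with predicted mortality, overall and by treatment group (11.2.1 and 13.2.1): "We will develop a severity model for predicting mortality based on the Tuhrim model". Neither section applies that comparison to craniotomy patients.

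SAP 8.0 classes analyses without specific hypotheses as exploratory, to be reported with descriptive statistics and confidence intervals. The craniotomy step does not appear in the list of measures in SAP 2.2.

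**The concern.** Whether an operation saved lives depends on how many of the same patients would have died without it. The SAP supplies that quantity by assumption, at its maximum, and then reads the answer from the survivors. The data enter only through mortality after craniotomy, so the result would look favourable whether the operation helped, did nothing or did harm.

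What is at stake is how the craniotomy result is read. SAP 5.4.1 justifies looking at craniotomy by noting that no trial has shown it to be beneficial. A percentage labelled life-saving, with a confidence interval around it, could be taken as evidence on exactly that question, although the interval would reflect only sampling error in survival and none of the uncertainty about what would have happened otherwise.

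**Working it through.** The documents give no figure for this analysis, so there is nothing to reproduce. The check is an identity.

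**Notation.** N patients have a craniotomy and D of them die. m1 = D/N is observed mortality after craniotomy. m0 is the mortality the same patients would have had without it.

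**The rule.** The SAP leaves the count undefined. With all N assigned to death, the frequency that follows is survivors over craniotomies:

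- reported frequency = (N − D)/N = 1 − m1
- net effect of craniotomy = m0 − m1
- overstatement = (1 − m1) − (m0 − m1) = 1 − m0

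The overstatement equals survival without craniotomy. It is zero only if m0 = 100%.

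**Inputs.** No document gives mortality for rescue-craniotomy patients. The values below are assumptions: 40% (the approximate 30-day mortality for ICH in Protocol 2.1), 60% (the 30-day mortality threshold for DSMB review in SAP 2.3.2) and 80% (assumed, because patients who deteriorate may fare worse).

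| Assumed m0 | Reported if no effect (m1 = m0) | True net effect | Reported if craniotomy adds an assumed 10 points of mortality | True net effect |
|---|---|---|---|---|
| 40% | 1 − 0.40 = 60% | 0 | 1 − 0.50 = 50% | −10 points |
| 60% | 1 − 0.60 = 40% | 0 | 1 − 0.70 = 30% | −10 points |
| 80% | 1 − 0.80 = 20% | 0 | 1 − 0.90 = 10% | −10 points |

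**In counts.** With an assumed 20 craniotomies and no effect, the expected number of lives saved under the rule is 20 × 0.60 = 12, 20 × 0.40 = 8 and 20 × 0.20 = 4. Even at 80% mortality the chance of at least one is 1 − 0.80^20 = 0.988.

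**One observed result, several truths.** Suppose m1 = 60%. The rule reports 40% whatever m0 is, while the net effect m0 − m1 is:

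- −10 points if m0 = 50%
- 0 if m0 = 60%
- +20 points if m0 = 80%
- +40 points only if m0 = 100%, which is the SAP's assumption

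**Is m0 = 100% supported?** Appendix 3 lists several serious reasons for surgery, and the life-saving wording is the last item in the list. Nothing there, or elsewhere in the documents, says that each such patient would otherwise die.

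**The case against.** The strongest defence is that this is a minor and openly labelled step. It is exploratory, it comes after a separate benefit comparison with two comparator groups, it announces its salvage premise, and it puts the life-saving term in quotation marks. It can be read as a best-case bound. Most of this stands and limits the weight of the point. It does not rescue the figure: the SAP does not call it a bound, and the earlier comparison is by treatment received, with no adjustment stated in that section for indication or for survival up to surgery, so it supplies no counterfactual here.

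Appendix 3 also fits a salvage framing better than a bare list of indications suggests. The ICP criterion applies under optimal medical management, and the word other in the final item may imply that the listed indications are themselves life-saving. So it would be too strong to say that the protocol contradicts the premise. It does not establish certain death, and that is enough.

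Two stronger readings are tempting, and the documents do not support them:

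- A reader might put the false life-saving frequency at 85–90%, since in phase II "Thirty-day mortality was 10% and 15% for the medical and surgical groups respectively". Those rates belong to whole arms, not to patients who deteriorated enough to need a craniotomy. The identity carries over; those numbers do not.
- A reader might infer that the death assignment will distort the comparison of randomised arms wherever rescue surgery is used unequally. No section applies it by randomised arm. SAP 5.4.1 groups patients by treatment received, and the clause that follows the assignment points to counting survivors.

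**Conclusion.** The step is wrong as written. The reported frequency equals 1 − m1, and it overstates the net effect of craniotomy by 1 − m0: 60, 40 or 20 points at assumed mortality without craniotomy of 40%, 60% or 80%. The direction holds at any m0 below 100%; the size is unknown, because the documents give no mortality for these patients. The conclusion rests on reading the undefined frequency as survivors over craniotomies, which is the natural count once everyone has been assigned to death.

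The reach is limited. The primary analysis in SAP 11.1 uses adjudicated mRS by assigned arm, so neither its result nor its type I error is touched. Nor does it follow that the trial's planned assessment of craniotomy benefit is this figure, because that is the as-treated comparison stated just before it. The point concerns one exploratory number that would carry a causal label it cannot support.

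**What to change.** In SAP 5.4.1:

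1. Delete the death assignment and the life-saving frequency.
2. Tabulate craniotomies by randomised arm and by timing, with observed mortality and mRS, and label the result as survival after craniotomy.
3. For these patients, show observed deaths beside deaths predicted by the severity model already planned in SAP 11.2.1 and 13.2.1. Report predicted minus observed without truncating at zero, so that possible harm stays visible.
4. Add a sensitivity range for mortality without craniotomy (m0) and report m0 − m1 across it, including values of m0 below the observed mortality. Do not use the all-survivors count as the upper limit of a benefit range, since that is the figure being removed.
5. State that a model built on baseline presentation may under-predict risk in patients who deteriorated later, so the comparison with prediction is descriptive.

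The cost is one paragraph, using data and a model already planned. No clinical rule changes. The downside is that the result becomes a description or a range instead of a single figure.
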